### 6.5.1. Data Review during the Study

Data will be analyzed while the trial is ongoing. An assessment committee will not be formed. Safety data will be reviewed by sponsor on a regular basis while participants are enrolled in the study.

Two safety data reviews are planned to occur during the Study GPHV. Such an interim safety review will not be considered as formal interim analyses. This review will be used to support dose decisions for subsequent cohorts to be enrolled. The interim data reviews will include the following:

- *Cohort 1 safety and tolerability data review*- all available safety and tolerability data up to at least Day 36 from at least [redacted] participants with obesity in Cohort 1 who received and completed at least 5 weeks of treatment, and
- *Cohort 2 safety and tolerability data review*- all available safety and tolerability data up to at least Day 36 from at least [redacted] participants with obesity in Cohort 2 who received and

completed at least 5 weeks of treatment and all available safety and tolerability data from Cohort 1 participants.

At the time of safety reviews, any available PK data may also be reviewed by sponsor.

## **6.6. Continued Access to Study Intervention after the End of the Study**

Not applicable.

## **6.7. Treatment of Overdose**

For this study, any dose of study intervention greater than [REDACTED] mg will be considered an overdose in Cohorts 1 and 3. Likewise for Cohort 2, doses above [REDACTED] mg will be considered an overdose.

In the event of an overdose, the investigator should

- contact the medical monitor immediately
- evaluate the participant to determine, in consultation with the medical monitor, if additional tests and treatment will be required
- closely monitor the participant for any AE/SAE and laboratory abnormalities until the participant is clinically stable or recovering
- obtain an unscheduled plasma sample for PK analysis if requested by the medical monitor (determined on a case-by-case basis), and
- document the quantity of the excess dose in the CRF.

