### 1.3. Schedule of Activities

## Study Schedule Protocol I8F-MC-GPHV

Visit Number	1 Screening	2 Baseline and Inpatient	3	4	5	6	7	8	9	10	11	12	13 = Final Follow- up	Early Discontinuation
Week	-4 to -1	1	2	3	4	5	6	7	8	9	10	11	12	at least 4 weeks but up to 6 weeks from Last Dose
Days	CCI													
Visit Interval Tolerance (Days)														
	
Comments: Participant and accompanying adult will be admitted to the inpatient unit on morning of Day 1 for medical assessments and baseline measurements prior to randomization and treatment. All participants will be closely monitored for safety and discharged earliest on Day 3. The inpatient stay may be extended by the investigator if it is necessary for the participant's clinical well-being.
													
Outpatient visit	X		X	X	X	X	X	X	X	X	X	X	X	X
	
Comments:
 
 
· For all participants - screening Visit 1, inpatient Visit 2 and outpatient Visits 3, 7, 10, and 12 must be performed in-clinic.
 
· For all participants who discontinued early - early discontinuation visit must be performed in-clinic.
 
· For Cohort 2 participants only - additionally, Visits 4 and 5 must be performed in clinic due to the necessity of tirzepatide dosing manipulations for preparing a CCI dose. This must be highlighted in the informed consent and assent forms for Cohort 2.
 
· All other outpatient visits, including final follow up (but not early discontinuation) may be performed remotely such as by telemedicine or by mobile healthcare services.
 
													
Adverse events & concomitant medication assessment	X	X	X	X	X	X	X	X	X	X	X	X	X	X
Physical examination /medical assessment	X	P, before discharge	P				P				X	X	X	X
	
Comments: Full physical examination at screening. Thereafter, assessments performed to include medical review and targeted, symptom-driven examination, as appropriate. Additional assessments may be performed at investigator's clinical discretion. P = predose measure that can be performed any time prior to dosing.
													
Height, weight, waist circumference, and body mass index	X	P				P					X	X	X	X
	
Comments: Height is required only during screening, Visit 1, and Visit 12. P = predose measure that can be taken any time prior to dosing.
													

Visit Number	1 Screening	2 Baseline and Inpatient	3	4	5	6	7	8	9	10	11	12	13 = Final Follow-up	Early Discontinuation

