	
Comments: Tirzepatide injection sites must be rotated along the 4 abdominal quadrants. Dosing may be performed by clinic staff during in-clinic visits. Self-administration by participant or parent or legal guardian is permitted after the investigator assessed them as being adequately trained. The dose increase will happen at the 5th dose as indicated in Figure GPHV.1.1
														
Tirzepatide sampling for pharmacokinetics (hrs)		12, 24		P		X: within 24 to 96 hrs postdose		P	X: within 120 to 168 hrs postdose		P	X	X	X	
	
Comments: Sampling time is relative to the latest dosing time. The actual date and time of the sampling and the most recent SC injection administered prior to collecting the sample must be recorded. Days 15, 36 and final follow-up or early discontinuation sample must be time-matched with immunogenicity sampling. No sample collection is needed if the participant discontinued before receiving tirzepatide. P = predose samples that should be collected within an hour prior to dosing.
														
Immunogenicity sampling		P	P					P					X	X	
	
Comments: Exact time of sampling must be recorded. Days 15, 36 and final follow-up or early discontinuation sample must be time-matched with pharmacokinetic sampling. No sample collection is needed if the participant discontinued before receiving tirzepatide. P = predose samples that should be collected within an hour prior to dosing.
														

Abbreviations: BMI = body mass index; CRF = case report form; ECG = electrocardiogram; hrs = hour; IBT = intensive behavioral therapy; I/E = inclusion and exclusion criteria; P = predose.

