## 2.3. Benefit/Risk Assessment

The risks of tirzepatide have been consistent with risks associated with other GLP-1 receptor agonists currently marketed. Potential risks include, but are not limited to, GI effects, acute pancreatitis (very rare), increases in heart rate, and hypoglycemic events (GLP-1 receptor agonist class effect).

No clinically significant safety or tolerability concerns have been identified during the clinical investigation of tirzepatide up to the single dose level of 5 mg or multiple weekly doses, when escalated up to 15 mg in adults. Based on this information, the highest starting dose of [REDACTED] mg and the highest dose of [REDACTED] mg tirzepatide to be administered in this study are reasonably anticipated to be tolerable in this group of pediatric participants with obesity.

Body weight is a known covariate affecting tirzepatide exposures based on population PK analysis in adult patients with T2DM. It is predicted that the exposure may be approximately 2-fold higher in the population with weight <50 kg compared to that in adults (weight  $\geq$ 50 kg); therefore, a more conservative initial starting dose of [REDACTED] mg will be adopted for participants in the lower body weight cohort (Cohort 2). This is a mitigation approach taken to reduce the risk of safety and tolerability issues before commencing another cohort of participants on an initial [REDACTED]-mg dose (Cohort 3).

Based on the known pharmacology of tirzepatide, participants with obesity may benefit from clinically meaningful weight reduction after 8 weeks of treatment. Potential risks, such as GI effects, acute pancreatitis, increases in heart rate, and hypoglycemic events, are consistent with the risks associated with currently available long-acting GLP-1R agonists in adults. These risks are clinically detectable and manageable and will be monitored throughout the study.

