#### 4.3. Justification for Dose

A starting dose of CCI mg accompanied by dose titration of CCI mg increments every 4 weeks (up to a maximum dose of 15 mg) was shown safe and well tolerated in adults with T2DM. The body weight of the pediatric participants in the higher body weight cohort (Cohort 1) in this study will overlap with the weight of adults studied in the T2DM program (weight around or higher than 50 kg). Thus, a starting dose of CCI mg for 4 weeks, followed by █ mg for 4 weeks, is planned for this pediatric population with body weight more than or equal to 50 kg.

The exposure in pediatric participants with weight  $< 50$  kg is anticipated to be up to 2-fold higher than the exposure in adults (weight range in Phase 3 studies in adults with T2DM: 43.1 to 227 kg), given that body weight was identified as a covariate on tirzepatide exposures in adults. Thus, a lower starting dose of CCI mg in this pediatric population with weight below 50 kg will be evaluated for tolerability and safety in Cohort 2. If the starting dose of CCI mg is well-tolerated, a starting dose of CCI mg will also be tested in Cohort 3 within a narrower weight range (40 to 60 kg, inclusive).

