### 6.1. Study Intervention(s) Administered

Participants will receive the SC doses of tirzepatide or placebo SC weekly. Matching placebo and tirzepatide CCI mg and E mg in prefilled syringes will be provided. For participants in Cohort 2 who are initiated on CCI mg dose, detailed instructions will be provided by the sponsor to clinical sites for preparing the required dose from the CCI-mg prefilled syringe and for placebo. As such, participants in Cohort 2 and their parents or legal guardian will have to be in-clinic (that is, remote visits will not be permitted) for Visits 2 to 5 for safety as well as for treatment preparation reasons.

Participants and legal guardians will receive a paper diary for the collection of study intervention details during remote visits. Paper diaries should be returned at the next site visit.

Table GPHV.6.1 shows the treatments administered.

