##### Events meeting the AE definition

Any abnormal laboratory test results (hematology, clinical chemistry, or urinalysis) or other safety assessments (for example, ECG, radiological scans, and vital signs measurements), including those that worsen from baseline, considered clinically significant in the medical and scientific judgment of the investigator (that is, not related to progression of underlying disease).

Exacerbation of a chronic or intermittent preexisting condition including either an increase in frequency or intensity of the condition.

New condition detected or diagnosed after study intervention administration even though it may have been present before the start of the study.

Signs, symptoms, or the clinical sequelae of a suspected drug-drug interaction.

Signs, symptoms, or the clinical sequelae of a suspected overdose of either study intervention or a concomitant medication. Overdose per se will not be reported as an AE/SAE unless it is

an intentional overdose taken with possible suicidal/self-harming intent. Such overdoses should be reported regardless of sequelae.

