### 10.3.3. Definition of Product Complaints

Product complaint

A PC is any written, electronic, or oral communication that alleges deficiencies related to the identity, quality, durability, reliability, safety, effectiveness, or performance of a study intervention. When the ability to use the study intervention safely is impacted, the following are also PCs:
 
 
• deficiencies in labeling information, and
 
• use errors for device or drug-device combination products due to ergonomic design elements of the product.
 
 
PCs related to study interventions used in clinical trials are collected in order to ensure the safety of participants, monitor quality, and facilitate process and product improvements.
 
Investigators will instruct participants to contact the site as soon as possible if he or she has a PC or problem with the study intervention so that the situation can be assessed.

An event may meet the definition of both a PC and an AE or SAE. In such cases, it should be reported as both a PC and as an AE or SAE.

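### Protocol 6.7 defines overdose by one fixed mg ceiling per cohort group, so an excess up to the raised dose at doses 1 to 4 does not call for the overdose steps

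*Protocol*

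**What the plan says.** Protocol 6.7 applies a mg ceiling to any dose in the study. There is one value for Cohorts 1 and 3 and one for Cohort 2, both redacted: "mg will be considered an overdose in Cohorts 1 and 3. Likewise for Cohort 2, doses above". The visible text does not mention week, visit, dose number or scheduled level. When a dose counts as an overdose, the investigator should contact the medical monitor immediately, evaluate the child with the monitor, watch closely for adverse events and laboratory abnormalities, take a PK sample if asked, and record the excess quantity in the CRF.

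The dose is not constant. The dosing comment in the Schedule of Activities (1.3) says: "The dose increase will happen at the 5th dose as indicated in" the study figure, which is not shown. Section 4.3 describes a starting dose for 4 weeks and then "mg for 4 weeks, is planned for this pediatric population with body weight more than or equal to 50 kg".

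In Cohort 2 the starting dose is not a ready-made syringe. Section 6.1 says that "detailed instructions will be provided by the sponsor to clinical sites for preparing the required dose from the" prefilled syringe, and requires Visits 2 to 5 to be in clinic. The Schedule of Activities gives the same reason: "additionally, Visits 4 and 5 must be performed in clinic due to the necessity of tirzepatide dosing manipulations for preparing a" dose at the starting level. The reason for starting lower is in 2.3: "It is predicted that the exposure may be approximately 2-fold higher in the population with weight <50 kg compared to that in adults".

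**The concern.** A fixed ceiling cannot match two dose levels. If it suits the second four weeks, it is too high for the first four, which is when the lower level is meant to protect the child while tolerability is established. A child could then receive more than the scheduled starting dose without the event being classed as an overdose.

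What would be lost is the clear instruction to call the medical monitor at once, evaluate and monitor, together with the record of the excess amount. Section 6.7 is the only place that asks for that amount. The case that matters most is Cohort 2, where each starting dose is drawn by hand and the start was lowered because exposure may be about 2-fold higher.

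**Working it through.** The plan states no figure to reproduce, and the mg values are redacted. The check is a case analysis plus a reading of the visit calendar.

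**1. Is there a gap?** Let S be the starting dose (doses 1 to 4), R the raised dose (doses 5 to 8), with S < R, and T the single ceiling, so that overdose means dose > T.

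- If T < R, every scheduled dose from the 5th on is an overdose. That cannot be intended.
- If T = R, a dose in the range (S, R] at doses 1 to 4 is above schedule but not an overdose. A dose above R is caught.
- If T > R, the uncaught range at doses 1 to 4 widens to (S, T], and an excess in (R, T] at doses 5 to 8 is also missed.

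So a workable T is at least R, and the gap exists whatever the redacted numbers are.

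**2. Does it apply to all cohorts?** Section 4.3 states two levels only for 50 kg and above. For Cohorts 2 and 3 the two levels follow from the dosing row of the Schedule of Activities, which is not split by cohort. In Cohort 2, hand preparation ends at Visit 5, just before the increase, which fits.

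**3. How many doses?** The 8 weekly doses fall on Days 1, 8, 15, 22, 29, 36, 43 and 50. The 5th is on Day 1 + 4 × 7 = Day 29.

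- Doses in the window: 4 of 8 = 50%.
- Cohort 2 hand-prepared doses in the window: Visits 2, 3, 4 and 5 = 4 of 4, all in clinic.
- Cohorts 1 and 3, doses that must be in clinic in the window: Days 1 and 8 = 2 of 4. Days 15 and 22 may be remote, and self-administration is allowed after training.

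**4. How large an excess?** Up to (R/S − 1) × 100% when T = R. R/S is redacted. As assumptions only, R/S = 1.5, 2 or 3 gives up to 50%, 100% or 200%.

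**5. What is scheduled after each early dose anyway?** (Schedule of Activities rows as they read in the extracted text, and Section 8.4.)

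| Dose (day) | Next vital signs and ECG | Next AE check | PK sample before next dose |
|---|---|---|---|
| 1 (Day 1) | 8 hours, then Day 8 | inpatient to at least Day 3 | 12 and 24 hours |
| 2 (Day 8) | 29 − 8 = 21 days | 15 − 8 = 7 days | predose Day 15 |
| 3 (Day 15) | 29 − 15 = 14 days | 22 − 15 = 7 days | none |
| 4 (Day 22) | 29 − 22 = 7 days | Visit 6, 1 to 4 days | 24 to 96 hours |

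**6. Does another section call for the same steps?**

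- 10.3.1: "Overdose per se will not be reported as an AE/SAE unless it is" intentional with possible self-harm intent. Signs or symptoms of a suspected overdose are AEs, so this route works once the child has symptoms.
- 6.1.2 and 10.3.3: a use error may be a product complaint. Without an SAE link, 8.3.1 gives 1 business day.
- 6.4: the dose is confirmed before clinic dosing, and syringes are reconciled with compliance records.
- 6.5: off-protocol dose modification is not permitted, but no clinical response to a dosing error is given.
- 8 and 8.3: immediate safety concerns and unusual events go to the sponsor, once someone recognises them as such.
- SAP 9: deviations are weighed for severity and impact when analysis populations are assigned.

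Each is a real control. None calls for the 6.7 steps when a child without symptoms receives too much at doses 1 to 4.

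**The case against.** The strongest reply is that a ceiling per cohort group is a coherent choice: 6.7 is already tailored to the lower-weight cohort, and a smaller excess is a deviation handled elsewhere. If the ceiling equals the raised dose, the child receives no more than is planned for the same child later. Section 2.3 also reports no clinically significant concern in adults at single doses up to 5 mg. Much of this stands, and it is why the weight is low. The adult evidence helps less than it seems to, because the study doses are redacted and exposure below 50 kg may be about 2-fold higher.

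The redaction could also hide a period-specific value. That cannot be excluded, but the surrounding sentence reads as one number per cohort group.

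A reader might infer more than the documents support, in three ways:

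- That an automatic safety trigger is lost. The 6.7 steps are what the investigator *should* do, and the PK sample is taken only on request.
- That the product-complaint route is closed unless the error comes from the device design. Section 10.3.3 names "use errors for device or drug-device combination products due to ergonomic design elements of the product" as an additional kind of complaint, and 6.1.2 lists use error without that condition.
- That injecting the whole source syringe in Cohort 2 goes unnoticed. This depends on redacted strengths: it falls in the gap if the syringe holds the Cohort 2 raised dose, but not if it holds more than the ceiling.

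**Conclusion.** The point holds as a low-weight, cheap improvement in safety handling. The 6.7 definition misses an excess above the starting level and up to the raised level at 4 of 8 doses. It matters most in Cohort 2, where all 4 of those doses are hand-prepared.

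The conclusion rests on three assumptions: each redacted box in 6.7 holds one number, the ceiling is at or above the raised dose, and the increase at the 5th dose applies to every cohort. The bound on harm needs one more, that the ceiling equals the raised dose; if it is higher, the bound fails.

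It would be wrong to read this as early overdoses going unmonitored. Larger errors are still caught by 6.7, and the inpatient stay, AE checks at every visit, predose confirmation, syringe reconciliation, PK samples after doses 1, 2 and 4, AE reporting of symptoms and deviation review cover part of the rest. The PK samples measure exposure, but 8.4 does not describe returning results to the investigator for immediate care. How often such errors occur cannot be estimated from the documents.

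**What to change.** In Protocol 6.7, define overdose as any administered dose above the dose level assigned to that participant for that administration under the protocol schedule. Use the same rule to set the level after a missed or interrupted dose, in line with 6.5, which resumes treatment at the scheduled level. Do not add a separate calendar-day cut-off: the increase is tied to the 5th dose, and once a dose is missed, dose number and study day no longer agree.

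For hand-drawn Cohort 2 doses, add a measuring tolerance set by the sponsor, so that trivial differences in drawing up are not classed as overdoses. A CRF field for the amount is needed only if none exists. The SAP does not change.

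The cost is a short change of wording and the tolerance, the usual amendment approval, and a few more dosing errors reported to the medical monitor. Scheduled doses 5 to 8 would still not be flagged.

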## **6.8. Concomitant Therapy**

Prior to therapeutic intervention, an investigator must review the study participant's vaccine record to evaluate the risk of under-immunization to the pediatric study participant.

In general, concomitant medication should be avoided. If the need for concomitant medication arises (for example, to treat an AE), inclusion or continuation of the participant may be at the discretion of the investigator, preferably after consultation with a sponsor CP or CRP/CRS or designee. Any medication used during the course of the study must be documented.

All participants on stable concomitant medication at the time of study entry, other than those that are prohibited, should continue their usual dose throughout the study unless deemed clinically necessary.

To mitigate potential GI symptoms due to tirzepatide and manage participants with poorly tolerated GI AEs, the investigator

- should advise the child to eat slowly or offer smaller meals, for example, splitting 3 daily meals into 4 or more smaller meals, and to stop eating when they feel full, and
- may prescribe symptomatic medication (for example, approved anti-emetic or antidiarrheal medication for children).

Any medication or vaccine (including over-the-counter or prescription medicines, vitamins, and/or herbal supplements) that the participant is receiving at the time of enrollment or receives during the study must be recorded along with

- reason for use
- dates of administration including start and end dates, and
- dosage information including dose and frequency for concomitant therapy of special interest.

The medical monitor should be contacted if there are any questions regarding concomitant or prior therapy.

Participants must abstain from starting any new prescription or nonprescription drugs after screening unless, in the opinion of the investigator in consultation with the sponsor CP or CRP/CRS, the medication is assessed as clinically necessary or is deemed unlikely to interfere with the study outcome.

If acetaminophen treatment is needed for pain management, the maximal allowed dose will be the amount as stipulated in the package insert for the body weight and age of the participant.

Other concomitant medication may be considered on a case-by-case basis by the investigator in consultation with the medical monitor if required.

## 7. Discontinuation of Study Intervention and Participant Discontinuation/Withdrawal

The discontinuation of specific sites or of the study as a whole is handled as a part of Appendix 1 (Section 10.1).

When necessary, a participant may be permanently discontinued from study intervention. If so, the participant, must complete early discontinuation procedures as shown in the SoA.

